### **SECTION I: RESEARCH PLAN**

1. **Statement of Purpose:** State the scientific aim(s) of the study, or the hypotheses to be tested.

**PRIMARY AIM 1.** To conduct a double-blind, placebo-controlled parallel group study to evaluate the efficacy of naltrexone HCI and bupropion HCI (NB) versus placebo in patients with binge-eating disorder (BED), stratified by obesity status (n=50 per cell, n=200 total).

- *Hypothesis 1.1.* We hypothesize that NB will be superior to placebo for reducing binge eating among patients with BED.
- Hypothesis 1.2. We hypothesize that NB will be superior to placebo for reducing weight among BED patients with obesity.
- Hypothesis 1.3. We will examine whether BED patients with and without obesity derive differential benefit of NB versus placebo on reducing binge eating (i.e., does obesity moderate outcomes).

**PRIMARY AIM 2.** To evaluate correlates and possible mechanisms underlying the effect of NB on binge eating among all participants (n=50 per cell, N=200 total). To evaluate the effect of NB on hypothalamic melanocortin and brain reward systems, eating behavior will be assessed with an established human laboratory paradigm designed to evaluate the ability to resist eating preferred high-caloric food and subsequent over-eating. We will evaluate potential mechanisms including eating peptides (leptin, ghrelin) involved in both homeostatic and hedonic aspects of eating, as well as food craving, mood, hunger, and control over eating.

Hypothesis 2.1. We hypothesize that potential medication-related changes in eating behavior, eating peptides and craving assessed in the laboratory will mediate clinical outcomes during the 12-week treatment period (i.e., rates of binge eating).

Hypothesis 2.2. We hypothesize that NB versus placebo will increase the ability to resist eating preferred high-calorie food, and will reduce overall calorie consumption in patients with BED.

Hypothesis 2.3. We will examine whether BED patients with and without obesity derive differential benefit of NB versus placebo with regards to their ability to resist eating or calories consumed (i.e., does obesity moderate outcomes).

**EXPLORATORY AIM 3**. To assess eating and drinking behavior, food craving, and mood 'in the field' in a subset of participants (n=60).

2. **Probable Duration of Project:** State the expected duration of the project, including all follow-up and data analysis activities.

September 2017 – September 2024

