**Baseline Assessment**: Participants will complete a physical exam, vitals, and routine laboratory blood work (including lipid profile, Hb1Ac, and liver function tests) at which time the study physician will review the subject's medical status and medical eligibility criteria. Patients will also have a urine screen for opiates. As part of the determination of eligibility, participants will complete two interviews, the MINI International Neuropsychiatric Interview-Version 7.0 (MINI) and Eating Disorder Examination (EDE) to generate psychiatric

diagnoses and detailed current eating disorder features and diagnoses. Other measures, for safety and establishment of baseline values, will also be obtained: BMI, vitals, eating behaviors, mood, and quality of life.

For a full description of instruments, see "Measures," which includes a grid depicting when each measure is administered. The baseline assessment will occur over 1-2 in-person meetings and is estimated to take a total of 2-3 hours in-person.

Randomization. Eligible participants who agree to participate and provide written informed consent will be randomized in equal proportions to one of the two treatments (using blocked randomization with random block sizes of 4 and 8 to obviate any secular trends). Gender will be balanced across cells (60% female). We will monitor randomization procedure and determine whether any systematic differences in demography (age, ethnicity/race) or clinical characteristics (psychiatric co-morbidity) become evident. We will consider adjustment to randomization if indicated (Kraemer & Fendt, 1990; Kraemer & Pruyn, 1990). The Biostatistician, [name], will be responsible for developing the randomization schedule in conjunction with the Investigational Drug Pharmacy (IDS), at Yale-New Haven Hospital. The IDS will randomize participants to medication groups. Research study staff (clinicians and outcomes assessors) and participants will all remain blind to the medication condition.

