### 13. **Statistical Considerations:** Describe the statistical analyses that support the study design.

Baseline demographic and clinical characteristics for the randomized groups will be compared using chi-square tests for categorical variables, and ANOVA or Kruskal-Wallis tests for continuous variables. Continuous variables will be examined for normality using normal probability plots and Kolmogorov-Smirnov test statistics. If normality is not satisfied, transformations or nonparametric alternatives will be considered. Dropouts and completers will also be compared. Primary analyses will be based on an intent-to-treat basis. Primary outcomes will be tested at the two-sided alpha 0.05 threshold. Secondary analyses will be adjusted for multiple tests using the Bonferroni correction basing the adjustment on the number of conceptually related statistical tests within each hypothesis.

Overall analysis strategy. Mixed-effects models [92] will be used to compare treatments. These models allow for different numbers of observations per subject, use all available data on each subject, and are unaffected by randomly missing data. A further advantage is the capacity to test and account for individual-difference contributions to the treatment outcomes (Cudeck, 1996; Cudeck & Klebe, 2002; Hedeker et al., 1996; Hedeker & Gibbons, 1996; Singer, 1998). They provide flexibility in modeling the correlation structure of the data. In models for each outcome in Aims 1 & 2, we will include obesity status (obese vs. non-obese) and treatment (NB vs. placebo) as between-subject effects, time (see Aim-specific study time points) as a within-subjects factor, and subject as the clustering factor. Across analysis, time-points associated with the 12-week treatment phase will be considered as primary outcomes, and all analyses will be repeated to examine change

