during the 12-month follow-up period. All possible interactions will be modeled and the following primary a priori contrast will be tested: 1) placebo NB vs. active NB. Least-square means will be plotted and compared post-hoc to interpret significant effects. Because we cannot a priori predict the shape of the response over time in each arm of the trial we will first treat time as a categorical predictor and will then test for polynomial trends over time. We will consider different error structures (e.g., AR1, CS, independence) and select the best fitting one based on Schwartz' Bayesian Criterion (BIC). We will compare dropout patterns between groups and if there are concerns of informative dropout or informative intermittent missing data, we will use pattern mixture models [93] to perform sensitivity analyses. Secondary models will include subjects with complete data. To test for assessment reactivity, we will evaluate whether biosensor assessment (yes/no; between-subject variable) moderates our primary outcomes in Aim 1 (as either a main effect, or interacting with medication). If this is found, then all subsequent analyses for Aims 1 & 2 will be limited to the sample (n=140) without the biosensor assessment.

Primary Aim 1. We will use the mixed models described above to test the effectiveness of NB medication for BED patients with and without obesity. The primary aims are to evaluate NB medication for (a) reducing binge eating frequency; and (b) in the patients with obesity, for reducing % weight loss. Significant NB main effects (regardless of obesity status) on frequency of binge eating will be considered supportive of our primary hypothesis. We also expect that NB will be associated with significantly greater reductions in % weight loss among the BED+obese group. In view of the factorial design, we will also be able to assess whether obesity status moderates reductions in binge eating frequency. These analyses will focus on 12-week outcomes. Secondary analysis will be repeated to examine change during the 12-month FU period.

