Secondary Aims. (a) Explore effectiveness of NB medication for BED patients with and without obesity on secondary outcomes: eating-disorder pathology (EDE global), eating behaviors (EDE, TFEQ, FCI, PFS), depression (BDI-II), psychosocial functioning (SF-36), metabolic measures (lipid profiles, HbA1c, blood pressure, heart rate) and "remission" and "relapse" from binge eating behaviors. The continuous secondary outcomes (e.g., EDE global, BDI-II, SF-36) will be analyzed using the same approach as for primary aim 1, and logistic regression will be used to compare proportion achieving remission from binge eating or relapse to binge eating. (b) Explore predictors, moderators, and mediators of primary outcomes (i.e., binge eating). In terms of treatment processes, we will attempt to replicate our findings regarding the prognostic significance of rapid response for behavioral and pharmacologic treatments ([name] et al., 2006, 2012, 2015; Masheb & [name], 2008). We will follow Kraemer's (2002) conceptual/statistical models for exploring predictors, moderators and mediators for binge eating. Per [name] et al. (2012), we hypothesize that overvaluation of shape/weight and depression levels to be significant predictors; such findings would inform future treatment prescription regarding this pharmacologic intervention. Per Kraemer (2002), we will explore if baseline characteristics predict/moderate treatment effects by testing for main effects and interactions in models specified above for primary outcomes. In terms of mediators, we will explore whether differential symptom changes during treatment are associated with subsequent longer-term primary outcomes. Repeated assessments of eating behaviors (EDEQ and TFEQ scales), and food-reward constructs (FCI, PFS) relevant to putative mechanisms of action for NB, will yield relevant change variables for analyses of mediation (i.e. testing subsequent changes in binge eating).

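### The Aim 1 model neither adjusts for baseline binge frequency nor ties the arms to a common baseline mean, and it judges Hypothesis 1.1 on a main effect over unlisted time points

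*Combined protocol and SAP*

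**What the plan says.** Section 13, under the overall analysis strategy, gives one mixed model for the outcomes of Aims 1 and 2: "obesity status (obese vs. non-obese) and treatment (NB vs. placebo) as between-subject effects, time (see Aim-specific study time points) as a within-subjects factor", with subject as the clustering factor. It continues: "All possible interactions will be modeled and the following primary a priori contrast will be tested: 1) placebo NB vs. active NB". On the coding of time: "we will first treat time as a categorical predictor and will then test for polynomial trends over time".

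Under Primary Aim 1, a significant main effect of NB on binge frequency, whatever the obesity status, counts as support for the primary hypothesis. The focus is the 12-week outcome. The aim-specific time points to which the model refers are not set out anywhere.

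The Measures section makes the EDE interview the primary method for assessing binge eating. The assessment grid (Figure 2) places the EDE at baseline, month 3, and the 6- and 12-month follow-ups. The self-report EDE-Q is also given at week 2 and months 1 and 2.

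Baseline characteristics appear in section 13 in two places only: the descriptive comparison of the randomised groups, and the exploratory predictor and moderator tests under Secondary Aims. For remission, "logistic regression will be used to compare proportion achieving remission from binge eating", and no covariate is named.

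**The concern.** Every participant has a baseline EDE because it determines eligibility. Conditioning on it normally reduces the variance of a later treatment comparison, and the plan does not do so. A mixed model does not supply the adjustment by itself. When all interactions are included and time is categorical, each arm has its own free baseline mean within each obesity group, and no information passes from baseline to the month-3 contrast through an assumption of equal baselines.

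The effect named as decisive adds a second problem. A main effect of treatment averages over whichever levels of time are in the model. If baseline is one of them, the average includes a value measured before randomisation, where no treatment effect can exist. Precision on the primary outcome is at stake, as is the quantity that the primary test estimates. Because the time points are unlisted, several readings also remain open, and the choice among them could be made after the data are seen.

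**Working it through.** **The plan's own figure.** There is none to reproduce: section 13 states no power, effect size, SD or baseline to month-3 correlation.

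**Inputs from the documents**
- Test level: "Primary outcomes will be tested at the two-sided alpha 0.05 threshold".
- Size: "stratified by obesity status (n=50 per cell, n=200 total", and patients are "randomized in equal proportions to one of the two treatments". Pooled over obesity status this is 2 × 50 = 100 per arm.
- Mean structure: "All possible interactions will be modeled", so the means are saturated.
- Measurement: baseline and month 3 are the only EDE values up to the end of treatment (Figure 2).
- Attrition in earlier BED drug studies: 20% to 38% (Data and Safety Monitoring Plan, treatment completion rates). That would leave 100 × 0.80 = 80 or 100 × 0.62 = 62 per arm.

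**Assumptions, not in the documents.** SD 1 at both times; correlation r = 0.3, 0.5 or 0.7; true month-3 difference d = 0.4 SD; complete data among those analysed.

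**Step 1: variance of each contrast, n per arm**
- Baseline as covariate, or common baseline mean: 2(1 − r²)/n
- Treatment by time (change score): 4(1 − r)/n
- Month-3 difference, unadjusted: 2/n
- NB main effect over baseline and month 3: (1 + r)/n, but its expected value is (0 + d)/2 = d/2

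Solving the two-time-point mixed model by generalised least squares gives these variances exactly. In the saturated model, treatment by time has the change-score variance and the month-3 least-squares-mean difference has the unadjusted variance. Only the common-baseline constraint (or a baseline covariate) reaches 2(1 − r²)/n.

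| n = 100 per arm | r = 0.3 | r = 0.5 | r = 0.7 |
|---|---|---|---|
| Adjusted | 0.0182 | 0.0150 | 0.0102 |
| Change score | 0.028 | 0.020 | 0.012 |
| Unadjusted month 3 | 0.020 | 0.020 | 0.020 |
| Averaged main effect (estimates d/2) | 0.013 | 0.015 | 0.017 |

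**Step 2: variance relative to adjusted**
- Change score, 4(1 − r) / [2(1 − r²)] = 2/(1 + r): 1.54, 1.33, 1.18
- Unadjusted, 1/(1 − r²): 1.10, 1.33, 1.96
- Averaged main effect, doubled so that it estimates d (variance × 4), 4(1 + r) / [2(1 − r²)] = 2/(1 − r): 2.86, 4.00, 6.67

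**Step 3: power, for illustration only (d = 0.4, two-sided 0.05)**

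| | r = 0.3, n = 100 | r = 0.5, n = 100 | r = 0.7, n = 100 | r = 0.5, n = 80 | r = 0.5, n = 62 |
|---|---|---|---|---|---|
| Adjusted | 84.3% | 90.4% | 97.7% | 83.2% | 73.0% |
| Unadjusted month 3 | 80.7% | 80.7% | 80.7% | 71.6% | 60.5% |
| Change score | 66.7% | 80.7% | 95.5% | 71.6% | 60.5% |
| Averaged main effect | 41.8% | 37.2% | 33.5% | 30.9% | 25.0% |

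**The case against.** The strongest reply is that the absence of adjustment is inferred from silence. Section 13 says that the models use all available data on each subject. With only one on-treatment EDE, a within-subject time factor needs baseline as a level, so baseline is probably in the outcome vector. This stands against a reading that a reader might adopt, namely that the plan discards baseline information. A change score uses baseline, though inefficiently, and its loss shrinks as the correlation rises (variance ratio 1.05 at r = 0.9). The reply does not rescue precision, because step 1 shows that a saturated model with baseline in the outcome gains nothing over a change score.

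A second reply is that the language on the shape of response and polynomial trends suggests more than two time points, perhaps from the EDE-Q. In that case the two-point ratios would not describe the model. That is fair, and it is a further reason to list the time points.

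Third, section 13 provides for comparing baseline characteristics, and the stopping-rules section for monitoring baseline differences. Neither is an adjustment of the treatment estimate.

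Fourth, a reader might infer that chance imbalance biases the primary analysis. Randomisation keeps the change-score and month-3 contrasts unbiased. A chance imbalance carries forward into the unadjusted estimate, but the change score subtracts the baseline, so the argument does not apply there in the same form.

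Fifth, percent weight loss, the other Aim 1 outcome, is already expressed relative to baseline.

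**Conclusion.** The point holds as a free improvement. The primary model as listed contains no baseline adjustment and no common-baseline constraint, and the effect named as decisive is not tied to month 3. For any correlation strictly between 0 and 1, with equal variances, both unbiased month-3 readings lose precision, by the factors in step 2. If the main effect is taken literally with baseline as a level of time, it targets about half the month-3 difference and is the weakest of the tests considered.

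The direction of the loss follows from the model terms. Its size rests on the assumed correlation, equal variances and complete two-point data, and the power table also on the assumed 0.4 SD.

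Three stronger conclusions are tempting but unsupported. One is a stated shortfall in power: the documents give nothing from which to compute it. Another is a much larger loss from analysing raw change in skewed counts: section 13 allows transformation or nonparametric methods when normality fails. The third is that the sample has no reserve for attrition: no sample-size derivation is given, so whether 50 per cell allows for dropout is unknown.

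**What to change.** In section 13, overall analysis strategy and Primary Aim 1:
- List the Aim 1 time points and state the role of baseline.
- For binge frequency, on the analysis scale chosen (transformed if skewed), and for the continuous secondary outcomes, take baseline out of the free arm-by-time means. Either enter it as a covariate or fit a common baseline mean across arms within each obesity stratum.
- Make the month-3 NB-placebo difference from that model the primary test of Hypothesis 1.1, in place of a main effect averaged over time.

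In section 13, Secondary Aims, add baseline binge frequency and obesity stratum to the remission logistic regression, and note that the odds ratio then becomes conditional on those covariates.

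The cost is a change of SAP wording. Baseline EDE is already collected on all participants, so no visit, measure or participant is added.

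### The error structures named for BIC selection all assume equal variance at every visit, so the SE for % weight change would probably be misstated; for binge frequency the effect is unknown

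*Combined protocol and SAP*

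**What the plan says.** Section I, item 13, under the overall analysis strategy, states: "Mixed-effects models [92] will be used to compare treatments". The between-subject effects are treatment and obesity status, time is the within-subject factor, and "subject as the clustering factor" completes the specification. No random intercept or slope is listed. Of these models it says: "They provide flexibility in modeling the correlation structure of the data". That speaks of correlation, not of variances that change by visit.

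On the covariance the plan says "We will consider different error structures (e.g., AR1, CS, independence) and select the best fitting one", using BIC. For the mean, "we will first treat time as a categorical predictor and will then test for polynomial trends over time", and "All possible interactions will be modeled".

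Under Primary Aim 1, the second outcome is "b) in the patients with obesity, for reducing % weight loss", and the analyses are said to focus on 12-week outcomes. Success for binge eating is defined separately: "Significant NB main effects (regardless of obesity status) on frequency of binge eating will be considered supportive of our primary hypothesis". The assessment grid (Figure 2) shows weight at baseline, week 2 and months 1, 2 and 3. The EDE, the primary binge-eating measure, appears only at baseline and month 3 within treatment.

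**The concern.** In their standard forms AR1, CS and independence each carry a single variance parameter. With time categorical and all interactions fitted, the week-12 difference is essentially a difference of week-12 means, but its model-based SE uses a variance pooled over all visits. % change from baseline is zero for everyone at baseline by construction and spreads out afterwards. Pooling the narrow early visits with week 12 makes the week-12 SE too small.

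BIC ranks only the candidates it is given. If they all share the equal-variance assumption, selection cannot remove the error. At stake is the type I error of Hypothesis 1.2 (weight in participants with obesity) if it is tested at week 12, or its power if the contrast is averaged over visits and AR1 is chosen.

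**Working it through.** The documents give no power calculation and no SD by visit, so there is no stated figure to reproduce. From the documents: two-sided alpha 0.05, 50 per arm in the obesity stratum, and post-baseline weights at weeks 2, 4, 8 and 12 (months 1, 2 and 3 read as weeks 4, 8 and 12). **All SDs and correlations below are assumptions**, as are complete data and equal covariance in the two arms.

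**Formulas.** True week-12 SE = SD12 × √(2/n). Under independence, and under CS with complete data, the model SE replaces SD12² by the mean of the visit variances, so

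ratio = √(mean variance / SD12²), actual alpha = 2 × (1 − Φ(1.96 × ratio)).

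For AR1 the limiting fit was found numerically by minimising log|V| + tr(V⁻¹S), where S is the assumed true covariance. BIC used N = 100 subjects.

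**Worked case, steep rise (SDs 1.2, 1.8, 3.0, 4.0).** Mean variance = (1.44 + 3.24 + 9 + 16)/4 = 7.42. CS ratio = √(7.42/16) = 0.681, alpha 18.2%. The true SE is 4 × √(2/50) = 0.80, against 0.681 × 0.80 = 0.54 from the model. BIC prefers AR1, which gives ratio 0.706 and alpha 16.6%.

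**Worked case, mild rise (SDs 2.5, 3.0, 3.5, 4.0).** Mean variance = 43.5/4 = 10.875. CS ratio = √(10.875/16) = 0.824, alpha 10.6%.

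**Worked case, random slope.** Slope SD 3.5 by week 12 and residual SD 0.8 give visit variances 3.5² × (t/12)² + 0.64, so SDs of about 1.0, 1.4, 2.5 and 3.6.

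| Assumed truth for % weight change | BIC choice of the three | Week-12 SE, model/true | Actual alpha | Visit-averaged SE, model/true |
|---|---|---|---|---|
| SD 1.2 to 4.0, constant correlation 0.8 | AR1 (965.5; CS 1017.5) | 0.71 | 16.6% | 1.05 |
| SD 2.5 to 4.0, constant correlation 0.8 | CS (1043.4; AR1 1069.3) | 0.82 | 10.6% | 1.00 |
| SD 2.5 to 4.0, correlation 0.8 decaying by visit | AR1 (1069.3; CS 1137.9) | 0.83 | 10.4% | 1.02 |
| Random slope, slope SD 3.5 | AR1 (818; CS 932) | 0.69 | 17.4% | 1.14 |

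Varying the slope SD from 2.5 to 4.5 gives week-12 ratios of 0.69 to 0.70 (alpha 17.0 to 17.5%) and averaged ratios of 1.09 to 1.16 under AR1. In 4,000 simulated trials with SDs 1.0, 1.4, 2.5 and 3.6, BIC chose AR1 every time. The week-12 test rejected 17.9% of the time, with Monte Carlo SE √(0.179 × 0.821/4000) = 0.6 points. An unstructured covariance rejected 4.9%.

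**Does BIC find a better structure if offered one?** For weight, yes. With constant correlation 0.8, heterogeneous CS scores 713.6 against 965.5 (steep) and 993.4 against 1043.4 (mild).

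**Binge frequency.** With the EDE at two visits, SDs 12 then 8 give √((144 + 64)/2)/8 = 1.27 (alpha 1.2%). A flat SD gives 1.00 (5%). SDs 10 then 12 give √((100 + 144)/2)/12 = 0.92 (7.1%). With five visits and SDs 12, 10, 9, 8, 8, the CS ratio is √(90.6)/8 = 1.19 (alpha 2.0%). For an NB effect averaged over visits, CS gives ratio 1.000 in every scenario examined.

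**The case against.** The strongest reply is that the three structures are only examples. The sentence opens its list with e.g., so an analyst may add an unstructured or heterogeneous structure, and for weight BIC would then prefer it. This stands as far as it goes: the documents do not confine the analysis to these three, and a reader who infers that they do goes too far. But it leaves the validity of a primary test to an unrecorded choice of candidates, and every structure actually named has the same fault.

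Second, a mixed model may include a random slope, which lets the variance change by visit even with independent residuals. That would largely cure the week-12 problem for weight (ratio 0.96 to 1.02). It also stands, but no random slope is specified.

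Third, the plan does not clearly name a week-12 contrast: 12-week outcomes may mean the whole treatment phase. For a visit-averaged contrast CS is right with complete data, so the inflated type I error does not carry over. AR1, chosen in three of the four tabulated patterns, then overstates the SE. With weaker constant correlation (0.6) and the steep SDs, that overstatement disappears.

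Fourth, item 13 allows transformations or nonparametric alternatives. Their trigger is non-normality, which rising but normal spread would not set off. For binge counts they might well apply and might stabilise the variance.

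**Conclusion.** The point holds for % weight change in participants with obesity. As named, the candidate structures would misstate the SE of a week-12 contrast: about 0.69 to 0.83 of the true value, with 5% becoming about 10 to 17%. If the contrast is averaged over visits and AR1 is chosen, the SE is mostly about 1 to 16% too large; under CS it is correct. That the spread rises from zero follows from the definition of the outcome. How steeply it rises is assumed, and so are the correlations.

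Two stronger readings are not supported. A reader might infer that the binge-frequency SE is also wrong. With no SD by visit, the EDE only at baseline and month 3 on treatment, and success judged on an NB main effect, the error may run in either direction or be nil. A reader might also take about 17% as the trial's type I error. It is the upper end under steep assumed growth, a week-12 contrast, no random slope and only the three named candidates.

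Dropout was not modelled. The Data and Safety Monitoring Plan cites 20 to 38% attrition in earlier BED drug studies. With that much missing data, a misspecified covariance could also affect the point estimate. This should be settled before unblinding, but it does not undermine the design.

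**What to change.** Replace BIC selection among equal-variance structures with a pre-specified unstructured covariance for the repeated on-treatment visits, with Kenward-Roger degrees of freedom. For % weight change, model post-baseline visits only, since the baseline value is a constant zero. Name one fallback if the model does not converge: a heterogeneous-variance structure with sandwich SEs. State any random effects, and say whether the primary weight contrast is at week 12 or averaged over visits; an unstructured covariance serves both. At minimum, add unstructured and heterogeneous structures to the BIC candidates.

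The cost is SAP wording and some extra parameters. Four visits need 4 × 5/2 = 10 covariance parameters and five visits need 15, against 2 for AR1 or CS. That is affordable with 100 to 200 participants, though dropout makes use of the fallback more likely. If the variance is in fact flat, essentially nothing is lost.
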